Despite these suggested therapeutic benefits of combined thermal ablation and embolization techniques, little is known about the prognostic effects of MWA + TAE in early-stage HCC. To our knowledge, no RCTs have compared the combination therapy (MWA + TAE) with monotherapy (MWA alone) in this selective cohort. The efficacy of MWA in combination with TAE as a prophylactic treatment to reduce recurrence in HCC patients with a small tumor burden is unknown. Moreover, the optimal protocol and timing for MWA combined with TAE as a treatment for early stage HCC has yet to be determined. For all of these reasons, RCTs are required to examine the feasibility as well as the possible therapeutic and/or survival benefits of combination MWA + TAE in selected patients with early-stage HCC.

STUDY DESIGN

Objective

This single-center, prospective RCT is designed to compare the outcomes and clinicopathologic results of blunt transarterial embolization (TAE) and microwave ablation (MWA) combination therapy with MWA monotherapy for the treatment of early (stages 0 and A) hepatocellular carcinoma (HCC). The primary aim of this study is to test the following hypothesis: 2-year intrahepatic disease-free survival does not differ between patients receiving the experimental therapy (MWA + TAE) and patients receiving the standard therapy (MWA alone) as treatment for early-stage HCC. Secondary aims are: 1) to determine the clinical feasibility of TAE + MWA in HCC patients with a small tumor burden using patient demographics and disease characteristic data and 2) to determine the effect of TAE on radiographic tumor characteristics in this patient cohort.

The primary outcome is 2-year intrahepatic disease-free survival, which is measured from time of randomization and is defined as the absence of local or regional recurrence of HCC as determined by diagnostic imaging. *Local recurrence* is defined as an enhancing lesion contiguous with the ablation zone that is present on subsequent imaging but was not present on the initial postablation scan. *Regional recurrence* is defined as hepatic recurrence that is not adjacent to the ablation site.

Secondary outcome measures include:

- Patient and disease characteristics (Table 1)
- 1-year, 2-year, 3-year, and 5-year overall survival;
- 1-year, 3-year, and 5-year intrahepatic disease-free survival;
- Number of TAE procedures required (for multilobar lesions or repeat effect)

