- Toxicity induced by TAE and or MWA using the latest published full version of Common Terminology Criteria for Adverse Events ([CTCAE v5.0](#) is slated for release in October 2015; [CTCAE v4.0](#) is available currently)
- 1-month and 3-month postoperative morbidity using the Clavien-Dindo Classification of Surgical Complications²⁷ (Appendix II);
- 1-month and 6-month postoperative mortality

- Ablation characteristics including tumor location by hepatic segment, proximity to a portal pedicle, number of applications, power settings, and ablation duration (per application and per tumor)
- Radiologic tumor observations applied to the Liver Imaging Reporting and Data System (LI-RADS) criteria at 4-6 weeks post-ablation, every 3 months for the first 2 years, and every 6 months thereafter
- AFP levels: baseline (preoperative/at diagnosis), 4-6 weeks post-ablation and TAE, every 3 months for the first 2 years, and every 6 months thereafter
- Return of bowel function (days), subdivided in: time until first stool, introduction of liquid or solid diet;
- Length of hospital stay (days);
- Length of ICU stay (days);
- 30- and 90-day readmission rates;
- Return to normal activity (days), i.e., return to full activity, work, or sport;
- Preoperative (baseline), 6-month and 1-year postoperative quality of life (QOL), using the Standard form 36 (SF-36 v 1.0) customized for HCC
- For those patients who go on to resection:
 - Duration of resection operation (minutes), defined as incision to dressing time;
 - Correspondence between pre-randomization clinical/radiologic/laboratory evaluation and intraoperative findings

Methods

Patient Eligibility and Allocation

Eligible patients will be identified in collaboration with the Levine Cancer Institute (LCI) at Carolinas Medical Center (CMC). The Institute functions as a series of integrated cancer programs distributing high-quality cancer care system-wide and houses nine cancer clinics, infusion therapy, palliative care and clinical trials, and state-of-the-art technology to connect member institutions across the Carolinas and worldwide. CMC is a high-volume center for the treatment of hepatocellular carcinoma and is one of only a few hospitals across the nation to utilize minimally invasive microwave ablative therapies to treat liver cancer. Approximately 60 MWA and several hundred TAE procedures are performed annually

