All operative MWAs will be performed in a laparoscopic or robot-assisted laparoscopic setting by one of four hepatobiliary surgeons with extensive experience with intraoperative US guidance and hepatic ablation ([name]). Care will be taken to create ample distance between the microwave near-field and any adjacent structures (diaphragm/heart, stomach/esophagus, colon, duodenum, gallbladder) by mobilization of the liver. All ablations will be guided by intraoperative ultrasound (BK Medical A/S, Herlev, Denmark) with care taken to allow for complete tumor treatment while preserving adequate distance between the microwave near-field and adjacent intrahepatic structures (portal pedicles, hepatic veins). Ablations will be performed with a 2.45-GHz generator with a 1.8-mm-diameter transcutaneous antenna (Acculis pMTA Accu2i; AngioDynamics Inc., Denmead, Hampshire, UK).

Operative variables will be recorded per patient, and individual ablation characteristics including tumor location by hepatic segment, proximity to a portal pedicle, number of applications, power settings, and ablation duration will be recorded for each individual tumor. A clearly demarcated zone of color flow Doppler activity will be visualized within 30 s of initiating the ablation to assure that the target is within the microwave ablation zone. Patients will be observed carefully, and analgesia will be administered per standard protocol if necessary.

Postprocedural Strategy

Division-specific standard guidelines will be applied to the postoperative care of patients included in this study. Postoperative complications will be recorded and treated symptomatically. All patients will be closely followed up for disease progression with clinical and laboratory examinations 4–6 weeks after ablation/TAE procedures, then every 3 months for the first 2 years. At 4–6 weeks following TAE +/- MWA procedures, tumors will be assessed radiographically and characteristics will be reported according to the LI-RADS criteria and guidelines. Imaging techniques will then be performed every 3 months during the first 2 years postoperative and every 6 months afterward. In addition, AFP levels will be obtained every 3 months during the first 2 years postoperative and every 6 months afterward.

Data Collection

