Incomplete ablation is defined as enhancement present at the ablation border on arterial phase CT consistent with residual tumor on the initial post-ablation scan. Local recurrence is defined as an enhancing lesion contiguous with the ablation zone that is present on subsequent imaging but was not present on the initial postablation scan. Regional recurrence is defined as hepatic recurrence that is not adjacent to the ablation site. Metastatic recurrence is defined as extra-hepatic recurrence including lymph node metastases. Expected residual disease is defined as disease that was intentionally left

untreated at the initial MWA session. Further, liver-directed therapy is defined as any secondary hepatic ablation procedure for incomplete ablation or any recurrent disease. Survival will be calculated from the time of randomization until last recorded follow-up, liver transplantation, or death.

Intrahepatic disease-free survival time is defined as the time between randomization and absence of local or regional recurrence of HCC as determined by diagnostic imaging. Overall survival will be measured as time from randomization until last recorded follow-up, liver transplantation, or death from any cause. Perioperative mortality is defined as in-hospital mortality.

Quality of Life

Quality of Life (QOL) will be assessed prospectively in a subgroup of patients who undergo follow-up examinations in the outpatient clinic of our facility. The data will be collected for a maximum of 5 years postoperatively or until patient death. Regular follow-up checkups will be offered to patients at 2-, 3-, or 6-month intervals depending upon time elapsed from surgery, with frequency of checkups decreasing as postoperative period increases in duration.

Statistical Analysis

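### Quality of life is a secondary outcome without restriction, yet it is collected only in an outpatient-clinic subgroup settled after randomisation, so an arm comparison is not fully protected

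*Combined protocol and SAP*

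**What the plan says.** The secondary outcome list in the Objective section includes "Preoperative (baseline), 6-month and 1-year postoperative quality of life (QOL), using the Standard form 36 (SF-36 v 1.0) customized for HCC". It limits neither the patients nor the place of assessment.

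The Quality of Life section, under Data Collection, describes the assessment differently: "Quality of Life (QOL) will be assessed prospectively in a subgroup of patients who undergo follow-up examinations in the outpatient clinic of our facility". On duration it adds: "The data will be collected for a maximum of 5 years postoperatively or until patient death". On the visits it says: "Regular follow-up checkups will be offered to patients at 2-, 3-, or 6-month intervals depending upon time elapsed from surgery".

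The Postprocedural Strategy section covers the whole cohort: "All patients will be closely followed up for disease progression with clinical and laboratory examinations 4–6 weeks after ablation/TAE procedures". Thereafter the interval is 3 months until the end of year 2. The section does not say where these examinations take place and does not mention quality of life.

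The Statistical Analysis section applies intention-to-treat to survival and disease-free survival. It gives no analysis set, model, or rule for missing data or death for quality of life. The Patient Eligibility and Allocation section says that double-blinding is not possible.

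**The concern.** Randomisation makes the arms comparable as randomised. It does not do so for a subset formed later by who is followed in one particular clinic. If a patient's health, the burden of treatment or knowledge of the assigned arm affects attendance, the attenders in one arm may differ from those in the other for reasons other than the effect of treatment on quality of life. The experimental arm has an additional procedure and the treatment is known, so unequal attendance is possible.

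The trial is presented as a comparison of outcomes between the two therapies, so a reader will expect the quality-of-life scores to be compared by arm. Scores that were never collected at 6 and 12 months cannot be recovered afterwards.

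**Working it through.** The plan gives no figure to reproduce here: there is no sample size, standard deviation, target difference or attendance rate for quality of life. The check is therefore a comparison of sections, followed by illustrations under stated assumptions.

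**Sections side by side**

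- *Population.* The outcome list sets no restriction; the Quality of Life section restricts to a clinic subgroup. No other section widens collection to all randomised patients.
- *Timing of membership.* The subgroup is defined by follow-up, but the first score is preoperative. Staff cannot know at baseline who will later attend, so the two sections cannot both be followed as written unless everyone is given the baseline form.
- *Duration.* The outcome list ends at 1 year; the Quality of Life section runs to 5 years or death.
- *Visits.* Examinations every 3 months for all patients over 2 years already include months 6 and 12, if counted from the operation.

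**Loss of precision (attendance is an assumption)**

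With a fraction *f* of patients measured in each arm, the standard error of the arm difference grows by 1/√*f*:

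- *f* = 0.8: 1/√0.8 = 1.12, an increase of 12%.
- *f* = 0.6: 1/√0.6 = 1.29, an increase of 29%.

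The Sample Size section gives 50 patients per arm. At 80% power and two-sided α = 0.05, the smallest detectable standardised difference is (1.960 + 0.842) × √(2/*n*), with *n* measured per arm:

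- all measured, *n* = 50: 0.56 SD
- 80%, *n* = 40: 0.63 SD
- 60%, *n* = 30: 0.72 SD

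**Bias (attendance rates and correlation are assumptions)**

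Suppose there is no true effect, scores are standard normal, and a patient attends when a latent variable with correlation ρ to the score exceeds a threshold. The mean score among attenders is ρ × φ(*c*)/*f*, where *c* is the normal quantile at 1 − *f* and φ is the normal density. The factor φ(*c*)/*f* is 0.195 at *f* = 0.9, 0.350 at 0.8, 0.497 at 0.7 and 0.644 at 0.6. The spurious arm difference is ρ times the difference between the two factors:

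| Attendance by arm | ρ = 0.3 | ρ = 0.5 |
|---|---|---|
| 80% and 80% | 0 | 0 |
| 90% and 80% | 0.05 SD | 0.08 SD |
| 90% and 70% | 0.09 SD | 0.15 SD |
| 80% and 60% | 0.09 SD | 0.15 SD |

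In this model, equal attendance under the same mechanism gives no bias in the arm difference. Bias needs attendance, or its relation to health, to differ by arm.

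**The case against.** The strongest reply is that this is a single-centre trial with scheduled follow-up for everyone, so the subgroup may be almost the whole cohort. That is possible, and it prevents any claim about how large the harm is. It does not remove the problem: the restriction is written down, the place of follow-up is not stated, and nothing sets a minimum size for the subgroup.

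A second reply is that no between-arm analysis of quality of life is written. This is true. The comparison is inferred from a listed secondary outcome of a trial designed to compare outcomes.

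Third, even 20-point gaps in attendance give about 0.09–0.15 SD of bias in the illustration, well below the 0.56 SD that the trial could detect with everyone measured. This stands under those assumptions. It is a reason to keep the point in proportion, since the outcome is secondary and the primary endpoint is untouched.

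Some stronger readings are tempting but unsupported:

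- A reader might infer that patients select themselves and that the sicker ones drop out. The plan says only that checkups are offered; it gives no selection rule and no reason for non-attendance.
- A reader might infer that the more burdensome arm will look better. The direction of any bias is not known.
- A reader might infer that analysis cannot repair the loss. If the restriction applies to follow-up only, non-attenders would have a baseline score, and Table 1 lists Child-Pugh, MELD, complications and laboratory data. These would allow partial adjustment under a missing-at-random assumption, though not certainty.

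**Conclusion.** The concern holds as a correctable weakness in a secondary outcome. Followed as written, the Quality of Life section yields scores in a subset settled after randomisation, without double-blinding and with no stated analysis that would protect a comparison of arms. Such a comparison may be biased if attendance or its relation to health differs by arm.

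Neither the size nor the direction of bias can be derived from the documents. The 12–29% rise in standard errors rests on assumed attendance of 80% down to 60%; it measures lost precision and should not be read as a measure of bias. The disagreement between the two sections on population and duration needs no assumption.

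**What to change.** 1. Replace the subgroup sentence in the Quality of Life section with collection of the SF-36 from every randomised patient at baseline, 6 months and 1 year, wherever the patient is followed.
2. Give the form at the follow-up already scheduled in the Postprocedural Strategy section. Mail a self-completed form to patients not seen at the facility, use the telephone only as a back-up, and record the mode.
3. Report completion by arm at each time point.
4. In the Statistical Analysis section, specify a comparison by randomised arm adjusted for the baseline score. A mixed model is one suitable choice. State how missing scores and deaths are handled, and include a sensitivity analysis for scores that may not be missing at random.
5. Reconcile the outcome list and the Quality of Life section on population and on duration (1 year or up to 5 years). If collection beyond 1 year is kept, say what it is for.

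The cost is a modest amount of mailing and follow-up effort, with no new visits for patients already seen at the facility. Mixing modes may introduce a small measurement difference, which is why the mode should be recorded. If nearly everyone attends the clinic anyway, the change costs almost nothing.

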Patients alive at the time of analysis will be censored at the last follow-up examination or at liver transplantation. Univariate analyses will be performed using the log-rank test of equality for categorical variables and the chi-square test with Cox proportional hazard model for continuous variables to identify clinical variables (Child–Pugh class, Okuda class, Model for End-Stage Liver Disease (MELD) score, etiology of cirrhosis), tumor factors (extrahepatic disease, multicentric disease, tumor size, Milan criteria, AJCC tumor stage, AFP level), and treatment-related factors (TAE, complications, recurrence) predicting intrahepatic disease-free and overall survival. Survival and disease-free survival will be estimated using the Kaplan–Meier method and tested with the log-rank test following the intention-to-treat principle. Statistical analysis will be performed using SAS software (SAS Institute, Cary, NC, USA).

The analysis will be planned at a median follow-up of two years, with an interim analysis scheduled for 1 year after the first patient is enrolled or when 50% of total expected enrollment has been reached.

To improve patient selection in the future, additional exploratory analyses will be performed to identify potential prognostic factors. Table 1 details variables that will be included in a Cox proportional hazards regression model to obtain hazard ratios and 95% confidence intervals (CIs). All P values will be two-sided and a p value $< .05$ will be considered significant.

ETHICAL AND SAFETY CONSIDERATIONS

Protection of Patients

The techniques and procedures used in this study protocol are not investigational or provisional in nature; rather, they are established in the provision of care for patients of the HPB Division at Carolinas Medical Center. The therapeutic benefit of combination of TAE/MWA treatment in this patient population remains unknown and is the focus of this study. The additive risk for adverse events is expected to be equal to the individual risks of the study procedures in this protocol.

Standard Division-specific guidelines will be closely followed to ensure patient safety and clinical well-being during all procedures. Patients will be closely monitored for complications associated with MWA and TAE, including wound complications, hematologic toxicities, and others.

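### The plan's only censoring rule uses the last examination, not the last scan; applied to intrahepatic disease-free survival, it would count missed imaging as disease-free time

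*Combined protocol and SAP*

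**What the plan says.** **Event.** Under Objective, the primary outcome is measured from randomization and "is defined as the absence of local or regional recurrence of HCC as determined by diagnostic imaging". Sample Size repeats this.

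**Time.** Under Definitions: "Intrahepatic disease-free survival time is defined as the time between randomization and absence of local or regional recurrence of HCC". The same section ends overall survival at last recorded follow-up, transplantation or death. It gives no censoring date for intrahepatic disease-free survival.

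**Censoring.** Statistical Analysis has one sentence: "Patients alive at the time of analysis will be censored at the last follow-up examination or at liver transplantation". Later in the paragraph: "Survival and disease-free survival will be estimated using the Kaplan–Meier method and tested with the log-rank test". No section mentions the last evaluable scan or says how missed scans are handled.

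**Schedule.** Postprocedural Strategy plans "clinical and laboratory examinations 4–6 weeks after ablation/TAE procedures, then every 3 months for the first 2 years". It requires radiographic assessment at 4–6 weeks, and then: "Imaging techniques will then be performed every 3 months during the first 2 years postoperative and every 6 months afterward". Separately, under Quality of Life: "Regular follow-up checkups will be offered to patients at 2-, 3-, or 6-month intervals depending upon time elapsed from surgery". No imaging is stated for those check-ups.

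**The concern.** The last contact is a sound censoring date for overall survival, since a patient who is seen is known to be alive. It is not sound for an event that only a scan can show: freedom from recurrence is known up to the last evaluable scan and no further. Time after that scan, while the patient still attends, adds to the risk set but cannot yield an event, so it can only raise the Kaplan–Meier estimate.

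The wording has two further problems. Read literally, the censoring sentence covers everyone alive at analysis, which would censor a patient who is alive with a documented recurrence. The Definitions sentence does not repair this, because absence of recurrence is a state and not a dated event. At stake are the event and censoring dates of the primary endpoint, in a trial planned around a 10-point difference (80% against 90%).

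**Working it through.** The plan gives no figure for the effect of its censoring rule, so there is none to reproduce.

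**Inputs from the documents.** 2-year rates of 80% and 90%, and 50 patients per arm (Sample Size); 2 patients per month, so 100 patients take 50 months (Patient Eligibility and Allocation); the examination and scan schedules (Postprocedural Strategy).

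**Assumptions.** Constant recurrence hazard; every rate of missed or stopped scanning.

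**Step 1: compare the schedules.**

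| | First | To 2 years | After 2 years |
|---|---|---|---|
| Clinical and laboratory examinations | 4–6 weeks | every 3 months | not stated |
| Imaging | 4–6 weeks | every 3 months | every 6 months |

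Through the primary horizon the two coincide. A patient who follows the protocol has a scan with each examination, so last examination and last scan agree and the overstatement is 0.

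**Step 2: hand calculation with gaps.** Let a share f of an arm stop scans at month 12 but attend to month 24. With true 2-year rate S, the first-year rate is √S. In year 2 events are detected only in the share 1 − f, so

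estimate = √S × [f + (1 − f)√S], and excess = f × (√S − S).

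- S = 0.80: √S − S = 0.8944 − 0.80 = 0.0944. For f = 5, 10, 20, 30% the excess is 0.5, 0.9, 1.9, 2.8 points.
- S = 0.90: √S − S = 0.9487 − 0.90 = 0.0487. The excess is 0.2, 0.5, 1.0, 1.5 points.

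**Step 3: simulation.** Uniform entry over 50 months, analysis at month 50 (median follow-up about 25 months), scans on the protocol schedule, ablation assumed 5 weeks after randomization, and stopping times spread evenly over 24 months. Entries are the 24-month estimate under last-examination censoring minus that under last-scan censoring, in points.

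| Assumed scanning | True 80% | True 90% |
|---|---|---|
| Every examination has its scan | 0.0 | 0.0 |
| 10 / 20 / 30% of scans missed at random | 0.15 / 0.36 / 0.63 | 0.08 / 0.19 / 0.33 |
| 5 / 10 / 20 / 30% of patients stop scans but attend | 0.5 / 0.9 / 1.9 / 2.8 | 0.2 / 0.5 / 1.0 / 1.4 |

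If scan dates also scatter by about 2 weeks, the gap at a true 80% is 1.1 points with 10% stopping and 2.2 with 20%. Part of that arises because last-scan censoring itself then sits slightly low (80.5% and 80.3%, against 80.7% with nobody stopping).

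**Step 4: difference between arms.**

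- 10% stop in both arms: by the Step 2 formula 90.5 − 80.9 ≈ 9.5 points (unrounded) against 10. The simulation, with scattered dates, gives 9.2 under the written rule and 9.7 under last-scan censoring. The difference shrinks slightly.
- 20% stop in the 90% arm only: formula 91.0 − 80.0 = 11.0 against 10; simulation 10.6 against 9.5.
- 20% stop in the 80% arm only: formula 90.0 − 81.9 = 8.1 against 10.

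For scale, with 50 per arm and no censoring the standard errors are √(0.8 × 0.2/50) = 5.7 and √(0.9 × 0.1/50) = 4.2 points. For the difference it is √(0.0032 + 0.0018) = 7.1 points.

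**Step 5: an extra visit with all scans done.** With dates scattered by 2 weeks and a final unscanned visit 1–3 months after the last scan, the two rules differ by about 0.7 points at a true 80%. The examination rule gives 81.3–81.4%, equal to the share with no recurrence detected by 24 months under full scanning. That gap is therefore not an overstatement; last-scan censoring falls slightly below the target.

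**The case against.** The censoring sentence speaks of patients alive and names transplantation, which mirrors the overall-survival definition, so it may never have been meant for the primary endpoint. The exclusion criteria also use the word examination for a CT, so the last examination could include a scan. Through year 2 visits and scans share one schedule, and check-ups without stated imaging appear only in the quality-of-life section, for a subgroup. Plausible shifts are small beside a standard error of 5.7 points for an 80% rate.

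Much of this stands. It rules out the flat statement that the 2-year rate is overstated: no document shows that patients will attend without being scanned. It also rules out the inference that last visit and last scan must drift apart even with perfect attendance. They coincide to year 2, and the 6-month scan interval begins only after 2 years postoperatively, outside the primary horizon.

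It does not remove the point. If the sentence is for overall survival only, the primary endpoint has no censoring rule and no usable event date. If it covers both endpoints, as the shared Kaplan–Meier sentence suggests, it uses the wrong date for one of them. Either reading needs the same repair. The ambiguity of examination is a reason to name the scan.

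**Conclusion.** The point holds as a defect in the rule that can inflate the primary estimate; it does not show that the estimate will be inflated. The effect is 0 with full adherence. Under assumed gaps, at the plan's own rates of 80% and 90%, it is about 0.1–0.6 points for 10–30% of scans missed at random. If 5–30% of patients stop scans but keep attending, it is about 0.5–2.8 points (true 80%) or 0.2–1.4 points (true 90%). Every non-zero figure rests on an assumed adherence pattern and a constant hazard.

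Because treatment is not double-blind, a reader might infer that the log-rank comparison is biased. The documents do not support that: they give no sign of differential scanning, and equal loss slightly narrows the difference. Only unequal adherence moves it materially, by about 1 point in the simulated case of 20% stopping in the 90% arm alone.

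**What to change.** Split the rule by endpoint, before the interim analysis:

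- **Overall survival:** censor at the date last known alive. How transplantation is handled is a separate question.
- **Intrahepatic disease-free survival:** the event date is the first scan showing local or regional recurrence. Patients without one are censored at their last evaluable liver CT or MRI.
- **Definitions:** replace 'absence of' with 'first imaging-documented'.
- **Sensitivity analysis:** repeat the primary analysis with last-examination censoring. An interval-censored analysis could be added, since last-scan censoring is not exact when scan dates scatter.

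The cost is a few sentences of wording and slightly shorter follow-up time. Scan dates must be recorded with the tumor radiology data; Table 1 lists tumor radiology but not its dates. Last-scan censoring also assumes that patients who stop scanning have the same later recurrence risk as those who continue. No clinical procedure changes.
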